### **8.4.3 Pregnancy and assessments of fertility**

All female participants of childbearing potential will have a serum pregnancy test performed at Visit 1 and EOS along with monthly urine pregnancy tests. In case of a positive urine pregnancy result, a confirmatory serum pregnancy test will be performed at the local laboratory. See [Section 10.1.4](#) for details on pregnancies.

Medical documentation of oophorectomy, hysterectomy, or tubal ligation must be retained as source documents. Subsequent hormone level assessment to confirm the woman is not of childbearing potential must also be available as source documentation in the following cases:

1. Surgical bilateral oophorectomy without a hysterectomy
2. Reported 12 months of natural (spontaneous) amenorrhea with an appropriate clinical profile

In the absence of the above medical documentation, follicle-stimulating hormone testing is required of any female participant, regardless of reported reproductive/menopausal status at Screening/Randomization.

### **8.4.4 Other safety evaluations**

#### **8.4.4.1 Adverse events of special interest**

##### **8.4.4.1.1 Angioedema**

Angioedema is a type of abrupt swelling that occurs under the skin and/or mucous membranes and is often localized to the head, neck, throat, and/or tongue, but may occur elsewhere, including the genitalia and intestines. Severe cases may be associated with airway compromise. Although, the mechanism is not fully understood, bradykinin has been implicated as the putative mediator. Therefore, medications that raise the levels of endogenous bradykinin by inhibiting the enzymes responsible for its breakdown, such as ACE, aminopeptidase P, and NEP, may result in this potentially dangerous side effect.

Simultaneous inhibition of multiple breakdown pathways of bradykinin is thought to significantly increase the risk of occurrence of angioedema ([Sulpizio et al 2004](#)). [Section 4.1](#) details how to avoid the simultaneous inhibition of the ACE and NEP pathways at Visit 101 (Randomization). The method outlined in [Section 4.1](#) is expected to provide at least 36 hours free of significant simultaneous inhibition of NEP and ACE, thereby minimizing the potential risk of occurrence of angioedema. This 36-hour washout is expected to present minimal risk to participants, especially since all participants will continue using their other background HF medications during this period.

#### 8.4.4.1.2 Other adverse events of special interest

Other AEs of special interest that will be collected are arrhythmias, symptomatic hypotension, hyperkalemia, and renal dysfunction.

### 8.4.5 Appropriateness of safety measurements

Participants subjected to treatment with ACEIs or NEP inhibitors are at increased risk of angioedema, which warrant special safety measurements.

The remaining safety assessments are standard for this indication and participant population.

## 8.5 Additional assessments

### 8.5.1 Biomarkers

NT-proBNP will be measured in all participants in the Main Study at Randomization and Week 12 as a component of the primary endpoint.

In addition, for participants who consent to participate in the biomarker additional assessment, changes from Randomization to Week 6 and Month 8 will be analyzed for blood biomarkers related to CV function/injury, fibrosis, and remodeling, aiming to elucidate if biomarkers are associated with event risk or disease progression as well as the effect of the study drugs on these markers. It is estimated that a subset of approximately ~550 participants will be included in the biomarker analysis.

Biomarkers that will be measured may include, but are not limited to:

1. markers of myocardial remodeling: e.g. MMP-2, MMP-9, TIMP-1, PINP, and PIIINP
2. markers of myocardial fibrosis and injury: e.g. high-sensitivity troponin T (hsTnT), aldosterone, and sST2
3. markers of myocardial stress: e.g natriuretic peptides
4. *Trypanosoma cruzi* parasitemia and serology will also be measured in order to explore its association with clinical endpoints. Furthermore, the association of this parasitological biomarker with other biomarkers signatures will be explored

The analysis of circulating markers is also planned to examine the effect of sacubitril/valsartan on protein expression and may support the identification of biomarker signatures that characterize CCC disease progression and the response to treatment with sacubitril/valsartan.

In addition, the comparison with other patients cohorts are also planned (patients with HFrEF without CCC and patients with Chagas disease but without HFrEF) aiming to gain insights into CCC pathophysiology.

Instructions for sample collection, numbering, processing, and shipment will be provided in the laboratory manual.

## **DNA sampling/pharmacogenetics**

The study also includes an optional genetic research component which requires a separate informed consent signature if the participants agree to it. As permitted by local governing regulations and by IRBs/IECs, it is required as part of this protocol that the Investigator presents this option to the participant.

The purpose of genetic research is to determine biomarker signatures in order to gain insight into the molecular mechanisms that underlie CCC development (by comparing with other patient cohorts [patients with HFrEF without CCC and patients with Chagas disease but without HFrEF]) and treatment response. As technology changes over time, the most appropriate technology will be used at the time the exploratory genetic research is performed. This may include high density SNP array or the study of the entire genome.

## **DNA samples**

The use of DNA to search for biomarkers of disease and drug action is exploratory. Any results from this DNA study will not be placed in the participant's medical records.

To maximize confidentiality, all samples and the information associated with the samples will be double-coded to prevent the exposure of the participant's information and identity. This double-coding process allows Novartis to go back and destroy the sample at the participant's request. In addition, sample information is stored in a secured database while genetic data is stored in an independent secured database.

### **8.5.2 Holter monitoring**

The pathophysiology of CCC leads to ventricular arrhythmias which have been associated with high rates of morbidity and mortality ([Barbosa et al 2015](#), [Ribeiro et al 2012](#)).

In PARADIGM-HF, sacubitril/valsartan reduced the risk of resuscitated and non-resuscitated sudden death by 22% compared with enalapril ([Desai et al 2015](#)). In addition, in a study with 120 HFrEF patients with ICD, sacubitril/valsartan decreased ventricular arrhythmias and ICD shocks compared with ramipril or valsartan ([de Diego et al 2018](#)).

Therefore, considering the arrhythmia burden in participants with CCC and the potential antiarrhythmic effects of sacubitril/valsartan, Holter monitoring will be performed at Randomization and at Month 8 in a subset of approximately 400 participants.

Additional details of the Holter monitoring assessment are outlined in [Appendix 6](#).

### **8.5.3 Magnetic resonance imaging**

Myocardial delayed enhancement by MRI quantifies myocardial fibrosis in patients with CCC, which increases progressively according to the severity of the disease ([Rochitte et al 2005](#)).

Also, myocardial fibrosis seems to be an independent predictor of adverse long-term outcome in CCC, supporting the use of cardiac MRI in better risk-stratifying this population and possibly guiding therapy ([Senra et al 2018](#), [Volpe et al 2018](#)).

Therefore, in order to gain a better understanding of the potential impact of sacubitril/valsartan on cardiac structure, function, and fibrosis, MRI will be performed at Randomization and at

Month 8 in a subset of approximately 100 participants (approximately 50 from each treatment group) at selected study sites. Additional details of the MRI additional assessment are outlined in [Appendix 7](#).

## 9 Study discontinuation and completion

### 9.1 Discontinuation

#### 9.1.1 Discontinuation of study treatment

Discontinuation of study treatment for a participant occurs when study treatment is permanently stopped for any reason (prior to planned duration), and can be initiated by either the participant or the Investigator.

The Investigator must discontinue study treatment for a given participant if, he/she believes that continuation would negatively impact the participant's well-being.

Study treatment must be discontinued under the following circumstances:

- participant decision
- pregnancy
- use of prohibited treatment as per recommendations in the prohibited treatment section
- any situation in which study participation might result in a safety risk to the participant
- any laboratory abnormalities that in the judgment of the Investigator, taking into consideration the participant's overall status, prevents the participant from continuing participation in the study

If discontinuation of study treatment occurs, the Investigator should make a reasonable effort to understand the primary reason for the participant's premature discontinuation of study treatment and record this information.

Participants who discontinue study treatment or who decide they do not wish to participate in the study further should NOT be considered withdrawn from the study UNLESS they withdraw their consent (see withdraw of informed consent section.). **Where possible, they should return for the assessments indicated** in the assessment schedule. If they fail to return for these assessments for unknown reasons, every effort (e.g., telephone, e-mail, or letter) should be made to contact the participant/pre-designated contact as specified in the lost to follow-up section. This contact should preferably be done according to the study visit schedule.

If the participant cannot or is unwilling to attend any visit(s), the study site staff should maintain regular telephone contact with the participant, or with a person pre-designated by the participant. This telephone contact should preferably be done according to the study visit schedule.

After study treatment discontinuation, at a minimum, in abbreviated visits, the following data should be collected at clinic visits or via telephone/email contact:

- new/concomitant treatments
- adverse events/SAEs

The Investigator must also contact the IWRS to register the participant's discontinuation from **study treatment**.

#### **9.1.2 Withdrawal of informed consent**

- Participants may voluntarily withdraw consent to participate in the study for any reason at any time. Withdrawal of consent occurs only when a participant: does not want to participate in the study anymore, and
- does not allow further collection of personal data

In this situation, the Investigator should make a reasonable effort (e.g., telephone, e-mail, letter) to understand the primary reason for the participant's decision to withdraw his/her consent and record this information.

Study treatment must be discontinued and no further assessments conducted, and the data that would have been collected at subsequent visits will be considered missing.

Further attempts to contact the participant are not allowed unless safety findings require communicating or follow-up.

All efforts should be made to complete the assessments prior to study withdrawal. A final evaluation at the time of the participant's study withdrawal should be made as detailed in the assessment table.

Novartis will continue to keep and use collected study information (including any data resulting from the analysis of a participant's samples until their time of withdrawal) according to applicable law.

All biological samples not yet analyzed at the time of withdrawal will no longer be used, unless permitted by applicable law. They will be stored according to applicable legal requirements.

Participants who withdraw their consent to participate in the additional assessments will still be able to participate in the Main Study provided they keep their consent to this part.

#### **9.1.3 Lost to follow up**

For participants whose status is unclear because they fail to appear for study visits without stating an intention to discontinue or withdraw, the Investigator must show "due diligence" by documenting in the source documents steps taken to contact the participant, e.g., dates of telephone calls, registered letters, etc. A participant should not be considered as lost to follow up until due diligence has been completed or until the end of the study.

#### **9.1.4 Early study termination by the Sponsor**

The study can be terminated by Novartis at any time for any reason. This may include reasons related to the benefit/risk assessment of participating in the study, practical reasons (including slow enrollment), or for regulatory or medical reasons. In taking the decision to terminate, Novartis will always consider the participant welfare and safety. Should early termination be necessary, participants must be seen as soon as possible (provide instruction for contacting the participant, when the participant should stop taking drug, when the participant should come for a final visit) and treated as a prematurely withdrawn participant. The Investigator may be informed of additional procedures to be followed in order to ensure that adequate consideration

is given to the protection of the participant's interests. The Investigator or ARO depending on the local regulation will be responsible for informing IRBs/IECs of the early termination of the study.

## **9.2 Study completion and post-study treatment**

The study will be completed when reaching 302 CV events **or** if a recommendation is made by the DMC to prematurely stop the study. At the end of the study, all participants will return for the final end of study (EOS) visit (Visit 199) and be asked to return the remaining study drug.

The Investigator must provide follow-up medical care for all participants who complete the study and all participants who are prematurely withdrawn from study drug, or must refer them for appropriate ongoing care. This care may include continuation of treatment with commercialized available sacubitril/valsartan treatment or switching participants to ACEI/ARBs in addition to other guidelines recommended HF medications, according to the Investigators judgment. Due to the potential risk of angioedema when sacubitril/valsartan used concomitantly with an ACEI, ACEI therapy must not be restarted until 36 hours after discontinuing of sacubitril/valsartan.

Study completion is defined as when the last participant finishes their End-of-study Visit, and any repeat assessments associated with this visit have been documented and followed up appropriately by the Investigator, or in the event of an early study termination decision, the date of that decision (e.g., each participant will be required to complete the study in its entirety and thereafter no further study treatment will be made available to them).

All randomized and/or treated participants should have a safety follow-up call conducted 30 days after the EOS. The information collected is kept as source documentation. All SAEs reported during this period must be reported as described in [Section 10.1.3](#). Attempts to contact the participant should be recorded in the source documentation.

## **10 Safety monitoring and reporting**

### **10.1 Definition of adverse events and reporting requirements**

#### **10.1.1 Adverse events**

An AE is any untoward medical occurrence (e.g., any unfavorable and unintended sign [including abnormal laboratory findings], symptom, or disease) in a participant or clinical investigation participant after providing written informed consent for participation in the study. Therefore, an AE may or may not be temporally or causally associated with the use of a medicinal (investigational) product.

The Investigator has the responsibility for managing the safety of individual participant and identifying AEs.

Medical personnel qualified by ARO will be readily available to advice on study-related medical questions or problems.

The occurrence of AEs must be sought by non-directive questioning of the participant at each visit during the study. Adverse events also may be detected when they are volunteered by the

participant during or between visits or through physical examination findings, laboratory test findings, or other assessments.

Abnormal laboratory values or test results constitute AEs only if they fulfill at least one of the following criteria:

- they induce clinical signs or symptoms
- they are considered clinically significant
- they require therapy

Clinically significant abnormal laboratory values or test results must be identified through a review of values outside of normal ranges/clinically notable ranges, significant changes from Baseline or the previous visit, or values which are considered to be non-typical in participant with underlying disease. Investigators have the responsibility for managing the safety of individual participant and identifying AEs. Alert ranges for laboratory and other test abnormalities are included in [Appendix 1](#).

Adverse events must be recorded in the Adverse Events eCRF under the signs, symptoms or diagnosis associated with them, accompanied by the following information (as far as possible) (if the event is serious refer to [Section 10.1.2](#)):

1. severity grade
  - mild: usually transient in nature and generally not interfering with normal activities
  - moderate: sufficiently discomforting to interfere with normal activities
  - severe: prevents normal activities
2. relationship to the study treatment
3. duration (start and end dates)
4. whether it constitutes a SAE and which seriousness criteria have been met
5. action taken with study treatment

All AEs must be treated appropriately. Treatment may include one or more of the following:

- dose not changed
  - dose reduced/increased
  - drug interrupted/withdrawn
6. outcome, i.e., its recovery status or whether it was fatal. If the event is ongoing, an outcome of not recovered/not resolved must be reported

Conditions that were already present at the time of informed consent should be recorded in the medical history of the participant.

Adverse events (including laboratory abnormalities that constitute AEs) should be described using a diagnosis whenever possible, rather than individual underlying signs and symptoms.

Adverse event monitoring should be continued for at least 30 days following the last dose of study treatment.

Information about adverse drug reactions for the investigational drug can be found in the IB. Any new information regarding the safety profile of the medicinal product that is identified between IB updates will be communicated as appropriate, for example, via an Investigator

Notification (IN) or an Aggregate Safety Finding. New information might require an update to the informed consent and has then to be discussed with the participant.

### **10.1.2 Serious adverse events**

An SAE is defined as any AE (appearance of or worsening of any pre-existing one) undesirable sign, symptom, or medical conditions which meets any one of the following criteria:

- fatal
- life-threatening

Life-threatening in the context of an SAE refers to a reaction in which the participant is at risk of death at the time of the reaction; it does not refer to a reaction that hypothetically might have caused death if it were more severe (please refer to the ICH-E2D guidelines).

- results in persistent or significant disability/incapacity
- constitutes a congenital anomaly/birth defect
- requires inpatient hospitalization or prolongation of existing hospitalization, unless hospitalization is for:
  - routine treatment or monitoring of the studied indication, not associated with any deterioration in condition
  - elective or pre-planned treatment for a pre-existing condition that is unrelated to the indication under study and has not worsened since signing the informed consent
  - social reasons and respite care in the absence of any deterioration in the participant's general condition
  - treatment on an emergency outpatient basis for an event not fulfilling any of the definitions of a SAE given above and not resulting in hospital admission
- is medically significant, e.g., defined as an event that jeopardizes the participant or may require medical or surgical intervention to prevent one of the outcomes listed above

Medical and scientific judgment should be exercised in deciding whether other situations should be considered serious reactions, such as important medical events that might not be immediately life threatening or result in death or hospitalization but might jeopardize the participant or might require intervention to prevent one of the other outcomes listed above. Such events should be considered as "medically significant". Examples of such events are intensive treatment in an ER or at home for allergic bronchospasm, blood dyscrasias or convulsions that do not result in hospitalization or development of dependency or abuse.

All malignant neoplasms will be assessed as serious under "medically significant" if other seriousness criteria are not met.

Any suspected transmission via a medicinal product of an infectious agent is also considered a serious adverse reaction.

All reports of intentional misuse and abuse of the product are also considered SAEs irrespective if a clinical event has occurred.

### **10.1.3 Serious adverse event reporting**

To ensure the safety of participants, every SAE (excluding the study endpoints), regardless of causality, occurring after the participant has provided informed consent and either until the time the participant is deemed a screen failure or until 30 days following the last administration of study treatment must be reported to ARO/Novartis Safety within 24 hours of learning of its occurrence.

Information about all SAEs is collected and recorded on the (electronic) Serious Adverse Event Report Form; all applicable sections of the form must be completed in order to provide a clinically thorough report. The Investigator must assess the relationship of each SAE to each specific component of study treatment, (if study treatment consists of several components) complete the SAE Report Form in English, and submit the completed form within 24 hours to the ARO/Novartis Safety. Detailed instructions regarding the submission process and requirements for signature are to be found in the Investigator folder provided to each study site.

The following pre-defined study endpoints are excluded from the expedited reporting of AEs and SAEs:

- CV death
- HF hospitalization
- all-cause mortality
- sudden death or resuscitated sudden cardiac arrest
- ER visits due to HF (where intravenous therapy is required)

All follow-up information for the SAE including information on complications, progression of the initial SAE, and recurrent episodes must be reported as follow up of the original episode within 24 hours of the Investigator receiving the follow-up information. An SAE occurring at a different time interval or otherwise considered completely unrelated to a previously reported one must be reported separately as a new event.

If the SAE is not previously documented in the IB or Package Insert (new occurrence) and is thought to be related to the study treatment, an associate from Patient Safety Department may urgently require further information from the Investigator for health authority reporting. Novartis may need to issue an IN to inform all Investigators involved in any study with the same study treatment that this SAE has been reported.

Suspected unexpected serious adverse reactions (SUSARs) will be collected and reported to the competent authorities and relevant ethics committees in accordance with EU Guidance 2011/C 172/01 or as per national regulatory requirements in participating countries.

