## 2 Objectives and endpoints

**Table 2-1 Objectives and related endpoints**

Objectives	Endpoints
Primary	
To assess whether sacubitril/valsartan is superior to enalapril in improving a composite hierarchical outcome of: a) time to CV death, b) time to first HF hospitalization, c) relative change in NT-proBNP levels between Baseline and Week 12 in participants with HFrEF caused by CCC	The primary endpoint is the hierarchically ordered composite consisting of time to CV death, time to first HF hospitalization, and the relative change from Baseline to Week 12 in NT-proBNP levels
Secondary	
1. To test whether sacubitril/valsartan is superior to enalapril in delaying the time from randomization to first occurrence of hospitalization due to HF or CV death	1. A composite outcome consisting of time from randomization to the occurrence of the first HF hospitalization or CV death
2. To test whether sacubitril/valsartan is superior to enalapril in delaying the time to death from any cause (all-cause mortality)	2. Time from randomization to all-cause mortality
3. To test whether sacubitril/valsartan is superior to enalapril in delaying the time to the first occurrence of resuscitated sudden cardiac arrest or sudden cardiac death	3. Time from randomization to sudden death or resuscitated sudden cardiac arrest
4. To test whether sacubitril/valsartan is superior to enalapril in reducing the number of visits to ER for HF (where intravenous therapy is required)	4. Number of visits to an ER due to HF (where intravenous therapy is required)
5. To test whether sacubitril/valsartan is superior to enalapril in increasing the number of days alive out of the hospital	5. Number of days alive out of the hospital
6. To compare sacubitril/valsartan with enalapril as to their safety and tolerability in participants with CCC	6. Safety and tolerability parameters: 
 
a. physical examination (as described in Table 8-2)
 
b. vital signs
 
c. laboratory evaluations
 
d. electrocardiogram
 
e. pregnancy assessment
 
f. adverse events
 
g. serious adverse events
 
h. adverse events of special interest (angioedema, arrhythmia, symptomatic hypotension, hyperkalemia, and renal dysfunction)
 

[figure not shown]
Objectives	Endpoints
Exploratory	

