#### **10.1.3.1 Special reporting requirements**

In outcome studies, some of the efficacy endpoints potentially meet the requirements for SUSAR reporting. The regulations have allowed an exemption from expediting safety notifications from SUSAR cases, aimed at ensuring the validity of an outcome study (European Commission ENTR/CT13 Guideline 2006, Chapter 5.1.9. Managing adverse reactions/events in trials with high morbidity and high mortality diseases and where efficacy end-points could also be SUSARs; FDA Guidance 2012).

Therefore, Novartis will NOT expedite a report to competent authorities/relevant ECs and will NOT issue an IN for disease related endpoints and AEs commonly seen in study population, as described below. These events will be presented in the clinical study report at the end of the study.

- pre-specified disease-related endpoints
- cardiovascular death, HF hospitalization, sudden cardiac death, arrhythmogenic cardiomyopathy
- adverse events that are commonly seen in the study population with HF
  - in clinical studies evaluating treatments for high morbidity and/or high mortality disease states, Investigators may report AEs or SAEs that are commonly seen in the study population (Table 10-1). SAEs that are not study endpoints, such as known consequences of the underlying disease or condition under investigation, or events common in the study population, are anticipated to occur with some frequency during the course of the study, regardless of drug exposure

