**Table 10-1 Adverse events that are commonly seen in the study population (Chagas cardiomyopathy)**

CV events		Non CV events	
Unstable angina	Generalized edema	Arthralgia/arthritis	COPD (including bronchitis and emphysema)
Arrhythmia	Hypertension	Constipation	Cough
Transient ischemic attack	Hypotension	Diarrhea	Fatigue
Renal impairment	Peripheral edema	Headache	Sepsis
Chest pain	Syncope	Nausea	Nasopharyngitis
Dizziness/vertigo	Angina pectoris	Anemia	Pneumonia
Cerebrovascular accident	Dyspnea	Upper respiratory infection/insufficiency	Dementia

An external independent Data Monitoring Committee (DMC) (see Section 10.2.2) will be appointed and will review efficacy and safety data of the ongoing study on a regular basis. The opinion and recommendations from the DMC will be notified by Novartis as soon as possible to the competent authorities and the ECs where they qualify for expedited reporting.

If specifically requested by a local Health Authority, pre-specified endpoints (see above) that also meet the criteria for SUSARs will be expedited to this Health Authority. Investigator Notifications will not be issued for these events.

Any other SUSAR that does not meet the pre-specified disease-related endpoints as mentioned above will be reported to competent authorities and relevant ethics committees and issuance of an IN will occur.

Any SAEs experienced after the 30-day period following the last administration of study treatment should only be reported to ARO/Novartis Safety if the Investigator suspects a causal relationship to study treatment.

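### Protocol 10.1.3 can be read as releasing sites from 24-hour reporting of any death, while 10.1.3.1 keeps a SUSAR duty for fatal non-CV events

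*Protocol*

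**What the plan says.** Protocol 10.1.3 sets the investigator's duty. It covers "every SAE (excluding the study endpoints), regardless of causality, occurring after the participant has provided informed consent", and such an event "must be reported to ARO/Novartis Safety within 24 hours of learning of its occurrence". Routine reporting runs until 30 days after the last dose. The section then says: "The following pre-defined study endpoints are excluded from the expedited reporting of AEs and SAEs". Five items follow: CV death, HF hospitalization, "all-cause mortality", sudden death or resuscitated sudden cardiac arrest, and ER visits for HF that need intravenous therapy. The same section also says, without repeating the exclusion, that information on all SAEs goes on the SAE form and that the form is submitted within 24 hours.

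Protocol 10.1.3.1 sets out what the sponsor will not expedite to authorities and ethics committees, and when it will not notify investigators. It exempts two classes. The first is disease-related endpoints, given as "cardiovascular death, HF hospitalization, sudden cardiac death, arrhythmogenic cardiomyopathy". The second is events common in the population, listed in Table 10-1. After the table it adds: "Any other SUSAR that does not meet the pre-specified disease-related endpoints as mentioned above will be reported to competent authorities".

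Table 2-1 makes "Time from randomization to all-cause mortality" the second secondary endpoint.

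**The concern.** Exempting efficacy endpoints from expedited reporting makes sense in an outcome trial when the endpoint is the disease itself. All-cause mortality is broader than that. CV death and sudden death already have their own lines in the 10.1.3 list, so the main effect of adding all-cause mortality is to bring in non-CV deaths.

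At stake is how quickly Safety learns of a death that study drug may have caused. The sponsor keeps a duty to report SUSARs outside the disease-related endpoints, but that duty normally starts from the site's SAE form. Section 10.1.3 also places the investigator's assessment of relationship to study treatment with that form. If a site concludes that no form is due, both the notice and the causality opinion may come late.

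**Working it through.** No arithmetic applies, and the plan gives no figure to reproduce. The check is a comparison of the texts.

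**Step 1: is any death a study endpoint?** Yes, for deaths after randomization. The Table 2-1 endpoint has no limit by cause. The opening phrase of 10.1.3, "every SAE (excluding the study endpoints), regardless of causality", therefore covers it even before the list is reached.

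**Step 2: which reporting step does the exclusion apply to?** The opening sentence concerns reports to the ARO and sponsor Safety, so the exclusion applies at the site-to-sponsor step. That duty applies regardless of causality and has no expectedness test.

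**Step 3: do the endpoint lists agree?**

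| Item | 10.1.3 (site to sponsor) | 10.1.3.1 (sponsor to authorities, ethics committees, investigators) |
|---|---|---|
| CV death | exempt | exempt |
| HF hospitalization | exempt | exempt |
| Sudden death | exempt | exempt, as sudden cardiac death |
| All-cause mortality | exempt | not listed |
| Resuscitated sudden cardiac arrest | exempt | not listed |
| ER visit for HF with intravenous therapy | exempt | not listed |
| Arrhythmogenic cardiomyopathy | not listed | exempt |
| Table 10-1 events | not listed | exempt |

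**Step 4: trace two deaths through the rules.**

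- *Fatal angioedema.* Angioedema is an adverse event of special interest. Section 8.4.4.1.1 says severe cases may compromise the airway. Section 4.5.1 gives confirmed cases in PARADIGM-HF as 19 of 4203 on sacubitril/valsartan and 10 of 4229 on enalapril, without saying whether any was fatal. At the site step, the death fits the all-cause mortality line and can be read as exempt. At the sponsor step, angioedema is neither a listed endpoint nor in Table 10-1, so the case is reportable if it qualifies as a SUSAR.
- *Fatal sepsis or pneumonia.* At the site step, the same exemption can be read. At the sponsor step, both are in Table 10-1 and so exempt as common events, although the closing sentence on other SUSARs carves out only the disease-related endpoints. The mismatch is clearest for events outside Table 10-1.

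**Step 5: is 10.1.3 consistent with itself?** No. The opening sentence and the list exclude endpoints; the sentence on the SAE form speaks of all SAEs and keeps the 24-hour limit. There is also an anomaly at the end of 10.1.3.1. SAEs after the 30-day window are reported if the investigator suspects a causal relationship, and no endpoint exclusion is repeated there. Read literally, a death suspected to be drug-related has a clearer route to Safety after the window than during treatment.

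**The case against.** The strongest reply is that other text already brings most such deaths to Safety. Section 10.1.1 asks for events to be described by diagnosis and records a fatal result as the outcome. On that reading angioedema is the SAE, it is not on the exempt list, and only the mortality endpoint is exempt. A non-CV illness that was life-threatening or led to admission would usually be an SAE before death, and its progression is due as follow-up within 24 hours. The sentence on all SAEs points the same way. SAP 2.6.3.4 says each adverse event of special interest had its own form, and the DMC reviews safety data every 6 months.

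Much of this stands. It shows that a benign reading exists and that many non-CV deaths would probably arrive through an earlier report. It does not remove the ambiguity: nowhere does the protocol say that the fatal diagnosis is reported while only the endpoint is exempt. The special-interest form has no stated 24-hour limit, and six-monthly review does not replace prompt notice.

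Three stronger readings are tempting, and the documents do not support them.

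- A reader might infer that the two sections give sites opposite orders. They do not: 10.1.3.1 governs the sponsor's reports, and the conflict in instructions to sites lies within 10.1.3.
- A reader might infer that the sponsor cannot expedite such a death. The sentence on all SAEs and the diagnosis-based reading leave routes open. Whether fatal angioedema would count as unexpected depends on the Investigator's Brochure, which is not among the documents.
- A reader might want a number of unreported deaths. The documents give no expected non-CV death rate for this trial. Routine SAE reporting also stops 30 days after the last dose, and deaths that follow an already reported SAE would not be missed.

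**Conclusion.** The point holds as an inconsistency in wording with a possible safety consequence. As written, a fatal non-CV event outside Table 10-1 can be read as exempt from the site's 24-hour report, although the sponsor keeps a duty to report it if it is a SUSAR. Such a death may reach Safety late.

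This rests on a site taking the exclusion literally and on no earlier SAE report having been made for the same episode. The size cannot be stated as a count. The problem does not touch the primary or secondary efficacy analyses, because deaths are still captured and adjudicated as endpoints. It is worth correcting because it concerns participant safety and the correction is cheap.

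**What to change.** Four changes to the protocol text:

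1. In the 10.1.3 list, remove all-cause mortality, or limit it to deaths that the investigator attributes to a listed CV endpoint.
2. In the opening sentence of 10.1.3, exclude only the endpoints listed below it. Without this change the first edit fails, because all-cause mortality would still be excluded as secondary endpoint 2.
3. State that every other fatal event within the SAE reporting window is reported as an SAE within 24 hours, and bring the sentence on all SAEs into line with that.
4. Reconcile the endpoint lists in 10.1.3 and 10.1.3.1, including resuscitated arrest, ER visits for HF and arrhythmogenic cardiomyopathy.

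Endpoint capture and adjudication of all deaths stay unchanged. The cost is a protocol clarification, a site letter and some additional SAE forms.
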